6.0 Procedures Involved*

- 6.1 Study Design: Study #1: This is a randomized dose finding study of nVNS versus sham stimulation in patients with a history of Opioid Use Disorders (OUDs). This study will optimize dosing (N=20) by testing different stimulation duration parameters. We will measure how these different parameters affect drug craving using analogue scales (248) as well as physiological signals with wearable sensing devices.

6.2

Study #2 is also in patients with OUDs whose aim is to measure brain and biological correlates of nVNS versus sham in conjunction with exposure to drug use cues (N=20). Active and sham devices are assigned serial numbers by ElectroCore Inc. and delivered to the Data Manager who keeps the blind and assigns to subjects as they are recruited using a random number generator. Subjects then undergo nVNS or sham over one day in conjunction with control neutral versus drug use videos to stimulate craving in conjunction with nVNS or sham with brain imaging, measurement of biomarkers and collection of wearable sensing device data. We proceed to the UH3 phase which is a larger study in OUD patients if the goals of the UG3 phase are met per NIDA. Only the UG3 phase is covered here. We hypothesize a decrease in sympathetic function and interleukin 6 (IL-6, an inflammatory marker) enhanced anterior cingulate function with VNS.

- 6.3 All subjects undergo assessment with behavioral measures, including the SCID (245, 246), a craving measure called the Clinical Opiate Withdrawal Scale (COWS) (248), the SHAPS-C, NRS pain scale, Addiction Severity Index, The Snaith Hamilton Pleasure Scale-Clinician (251), the Subjective Units of Distress Scale (263) The Visual Analogue Scale (VAS) consists of 10-point lines anchored with "not at all" on one end and

PROTOCOL TITLE: Non-invasive Vagal Nerve Stimulation in Opioid Use Disorders

"extremely" on the other where participants report the extent to which they felt any craving for opiates, severity of withdrawal symptoms, and the extent to which the study intervention has helped to ease the cravings.

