10.0 Inclusion and Exclusion Criteria*

10.1 Inclusion and exclusion criteria are listed below. Potential participants will be screened for eligibility by a staff member. We will try to pre-screen subjects via phone using a verbal consent and a waiver of documentation when possible. Otherwise, potential subjects will come in for a screening visit. At the first visit, study staff will confirm eligibility using a checklist.

10.2 The Inclusion and Exclusion Criteria for Study #1: Subjects aged 18 and over who: 1) meet criteria for OUDs based on DSM-5 criteria. The Inclusion and Exclusion Criteria for Study #2: Subjects aged 18 and over who: 1) meet criteria for OUDs based on DSM-5 criteria; 2) have IV access.

Exclusion Criteria: 1) positive pregnancy test; 2) meningitis; 3) moderate traumatic brain injury; 4) neurological disorder or organic mental disorder; 5) history of loss of consciousness greater than one minute; 6) current pregnancy or breastfeeding for women; 7) current or lifetime history of schizophrenia, based on the SCID; 8) a history of serious medical or neurological illness, such as cardiovascular, gastrointestinal, hepatic, renal, neurologic or other systemic illness; 9) evidence of a major medical or neurological illness that is based on the clinical judgment of the study psychiatrist; 10) carotid atherosclerosis; 11) cervical vagotomy.

PROTOCOL TITLE: Non-invasive Vagal Nerve Stimulation in Opioid Use Disorders

Several of the above exclusions will be based on the clinical judgment of the study physician. If reviewed and deemed acceptable by the study physician some exclusions may not preclude participation.

10.3 The following populations will also be excluded from the research:

- Adults unable to consent
- Individuals who are not yet adults (infants, children, teenagers)
- Pregnant women
- Prisoners

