17.0 Data Management* and Confidentiality

17.1 We will use analysis of variance models with change in blood flow as dependent variable and absolute blood flow during control task as well as study group as explanatory variables. This analysis will assess differences in brain function according to diagnosis correcting for potential differences in baseline (control task) values. The ANOVA model will be blocked by the matching factor of past alcohol exposure. Analyses will be adjusted for whole brain blood flow. Additional control factors, including patients' age, age of onset of traumatization, years of education, IQ, OUD symptom level and duration of disease, use of oral contraceptive birth control, and smoking, will be entered in the model if they are significantly different between the study groups at an alpha level of 0.25, and/or if they are found to be confounders in the analysis, i.e., if they cause a change of >10% in the parameter estimate for study group when entered in the model. Adjusted means of blood flow will be computed for each combination of group and task to better describe the results. Point estimates and confidence intervals for the difference between groups will be assessed before and after including the covariates mentioned above in the model. Additional analyses will compare OUD patients with and without a history of co-morbid depression.

In all these analyses linear model assumptions, adequacy of fit, and presence of outliers will be checked by inspecting residual plots and influence statistics. Collinearity for variables included in the model will also be checked. Appropriate remedies will be applied, if necessary, to improve model fit and minimize collinearity.

Additional exploratory analyses will use subtraction analysis techniques to look for additional areas of activation for the purpose of generating hypotheses for future studies. Images of absolute blood flow will be subjected to a subtraction type analysis. Images will be realigned to the first image in the series and warped into a common anatomical space using methods described in the preliminary results. Images will be then analyzed using the general linear model of Friston for statistical analysis. The mean of blood flow scans within condition will be calculated and comparisons performed between conditions to assess blood flow with the condition. Areas of increased and decreased blood flow within patient group will be examined, as well as the interaction between

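### Section 17.1 picks covariates for the PET comparison by data-driven rules suited to non-randomised groups, blocks on an undescribed matching factor, and does not say which estimate decides

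*Combined protocol and SAP*

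**What the plan says.** Section 17.1 models change in blood flow on study group and control-task flow, with adjustment for whole-brain flow.

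- **Covariate entry.** Eight further factors are named: age, age when trauma began, schooling, IQ, OUD symptom level, illness duration, oral contraceptive use and smoking. The list is open-ended. These "will be entered in the model if they are significantly different between the study groups at an alpha level of 0.25", and/or "if they cause a change of >10% in the parameter estimate for study group when entered in the model".
- **Blocking.** "The ANOVA model will be blocked by the matching factor of past alcohol exposure".
- **Contrast.** "This analysis will assess differences in brain function according to diagnosis correcting for potential differences in baseline (control task) values".
- **Reporting.** Point estimates and confidence intervals for the group difference "will be assessed before and after including the covariates mentioned above in the model". Neither version is named as deciding.
- **Safeguard.** "Collinearity for variables included in the model will also be checked", with no threshold and no specific remedy.

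On design, section 6.2 says that for Study #2 the Data Manager keeps the blind and "assigns to subjects as they are recruited using a random number generator". Section 10.2 admits to Study #2 "Subjects aged 18 and over who: 1) meet criteria for OUDs based on DSM-5 criteria; 2) have IV access". The sample-size text in 17.1 sets 10 per group, nVNS against sham.

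**The concern.** The model reads as if written for a matched comparison of patients with controls. There, screening for imbalance and for change in the estimate is a way of looking for confounders. Study #2 randomises its groups, so any baseline difference between arms is due to chance and the 0.25 test has no confounding to find. The 10% rule looks at the outcome by arm to decide which model is fitted. With 20 participants, the covariate set, and so the estimate, would depend on chance and on the result itself.

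The plan then yields two estimates, unadjusted and adjusted for the selected factors, and does not say which one answers the question. Anterior cingulate function is part of the primary endpoint in section 4.1, and section 2.1 makes progression to the UH3 phase depend on meeting the UG3 goals.

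**Working it through.** **Which groups are compared.** Section 17.1 says study group and diagnosis, not nVNS and sham. Three passages support reading it as the randomised arms: PET is done only in Study #2 (6.5), every participant has OUD (10.2), and the sample-size text labels the groups as the two arms. This is a well-supported inference, not explicit text.

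**Reproducing the plan's figure.** Two-sided alpha 0.05, effect size d = 1.39, n = 10 per arm. Noncentrality = d√(n/2) = 1.39 × √5 = 3.11 on 18 df, which gives power 0.836. At n = 9 power is 0.79. The stated 10 per group reproduces for an unadjusted two-sample t test.

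**Imbalance rule alone.** With eight independent candidates under randomisation, the expected number admitted is 8 × 0.25 = 2. The chance of admitting at least one is 1 − 0.75⁸ = 0.90.

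**Change-in-estimate rule.** A candidate enters if |b_adjusted − b_base| > 0.10 × |b_base|. The threshold shrinks with b_base, so the rule admits more candidates the smaller the observed effect.

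**Residual degrees of freedom.** Intercept, arm, two flow terms and a two-level alcohol block leave 20 − 5 = 15. About three selected covariates leave 12.

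**Both rules together, simulated.** There were 6,000 trials per scenario with 10 per arm. The base model had arm, two fixed terms unaffected by arm, and a binary alcohol block unrelated to outcome. Each of eight independent candidates was screened singly and those selected were entered together. The documents give no R² values, so those below are assumptions. At d = 1.39:

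| R² fixed terms | R² candidates | Power, fixed model | Power, selected model | Covariates admitted | Disagree on significance |
|---|---|---|---|---|---|
| 0 | 0 | 0.756 | 0.606 | 2.8 | 0.21 |
| 0 | 0.3 | 0.753 | 0.664 | 3.2 | 0.24 |
| 0 | 0.5 | 0.761 | 0.715 | 3.3 | 0.25 |
| 0.3 | 0 | 0.881 | 0.746 | 2.6 | 0.18 |
| 0.3 | 0.3 | 0.878 | 0.830 | 2.9 | 0.16 |
| 0.2 | 0.5 | 0.837 | 0.834 | 3.2 | 0.20 |

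Monte Carlo standard error for power is about 0.004–0.006. Omitting the block gives the same pattern, with disagreement of 0.14–0.23.

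**Under no effect.** With or without the block, 5.1–5.9 covariates enter. Type I error is 0.042–0.069 for the selected model and 0.081–0.094 if either estimate may be claimed (standard error about 0.003).

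**Varying the assumptions.**

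- *Correlated candidates* (pairwise 0.4, effects in the same direction; 1,500 trials per scenario, with block). Fixed to selected power is 0.739 to 0.609 at R² (0, 0), 0.877 to 0.861 at (0.3, 0.3), and 0.838 to 0.897 at (0.2, 0.5). A separate run with correlated prognostic candidates gave 0.85 to 0.89. The loss can therefore become a gain of about 0.05.
- *Smaller effect.* At d = 1.0, disagreement is about 0.30 or more when the candidates are prognostic (0.34 and 0.36 in two runs). It is lower when they are unrelated to outcome.
- *Reading and/or as and.* The loss is 0.02–0.07.
- *Collinearity check.* If the remedy were to drop covariates until the arm's variance inflation factor is below 5, little would change, because that value is exceeded in about 1% of trials. A strict limit of 2 gives between a loss of 0.10 and a gain of 0.03.

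**Matching factor.** The sections on design (6.1–6.2), eligibility (10.2) and allocation (6.2) mention neither matching nor stratification on alcohol. Past alcohol exposure appears in the plan only in 17.1, and its levels are not defined.

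**Baseline term.** Section 6.2 pairs stimulation with both the neutral and the drug-use videos. Section 6.5 says stimulation is given during the videos without saying which. If the neutral videos are stimulated, control-task flow is measured after randomisation and can be affected by arm. It is both the model covariate and the reference for change, and the simulations above would not apply.

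**The case against.** This is a 20-person mechanistic study. The plan shows estimates and intervals on both sides of the adjustment, so any selection would be visible. Adjusting for chance imbalance at 10 per arm is not unreasonable in itself, and selection can help when candidates are correlated and strongly prognostic. All of that stands, and it limits how much weight power can carry. Visibility does not settle which estimate decides, however, and the two can differ on significance.

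Three stronger readings are tempting and not supported:

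- *The rules seriously inflate type I error.* The selected model alone gives 0.04–0.07. The upper end is above 5%, but modestly. Values of 0.08–0.09 need a claim on whichever estimate succeeds, which the plan does not announce.
- *The rules cost 0.15 in power, or push it below 0.80.* The large losses need candidates with little or no prognostic value. In three of the six tabulated scenarios the fixed model is already below 0.80. The range is not a bound.
- *The adjusted estimate is the deciding one.* The wording on entry into the model can suggest this, but 17.1 does not say so.

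The effect size of 1.39 is itself borrowed from amygdala responses to fear tasks, not from nVNS against sham in the anterior cingulate.

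**Conclusion.** The point holds and should be fixed. As written, 17.1 makes the PET model for a randomised comparison depend on chance imbalance and on the observed arm effect, blocks on a factor the design does not contain, and leaves the deciding estimate open. These facts rest on the text, plus the one inference that study group means nVNS or sham.

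The numerical consequences are illustrations only. They assume eight candidates, particular R² values and correlations, an effect size, and baseline terms unaffected by arm. The firmest of them are that more covariates enter when the effect is small, and that the two estimates often disagree. The direction of the power change is not established by the documents.

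**What to change.** 1. Settle the baseline first. Reconcile 6.2 with 6.5 on whether stimulation accompanies the neutral videos; this review takes no view on which is right. If it does, define baseline and change from an unstimulated scan, or redraft both together. State also which scan supplies whole-brain flow.
2. In 17.1, name one prespecified deciding model: arm, the baseline flow term and whole-brain flow. Remove both entry rules from it and report covariate-adjusted estimates as sensitivity analyses only. Forcing in all eight candidates is not a good alternative: simulated power with 10 per arm was 0.41–0.66.
3. Delete the alcohol term, or keep it as a prespecified covariate with defined levels. Call it a stratum only if the randomisation was stratified on it.
4. Throughout 17.1, including the exploratory image analysis and the sample-size text, replace the references to diagnosis, diagnostic group, and patients versus controls with the nVNS and sham arms.

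Items 2 to 4 are wording. Item 1 is a sentence if the neutral videos are unstimulated, and a real redraft if they are not. The cost is some precision if the dropped candidates are strongly prognostic (about 0.05 in power in one assumed scenario), and a chance imbalance would be addressed only in sensitivity analyses.

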PROTOCOL TITLE: Non-invasive Vagal Nerve Stimulation in Opioid Use Disorders

condition and diagnostic group. Images of t statistic will be created and surveyed for hypothesized regions (i.e. medial prefrontal cortex) where uncorrected z score values are greater than 2.86 (corresponding to a corrected p value of > 0.005).

Calculation of Sample Size

For calculation of sample size needed for PET measurement of anterior cingulate activation, we used values for blood flow in the amygdala (scaled to whole brain blood flow) based on previous pilot data. Fear-related tasks resulted in a $6.9 + 4.8\%$ increase in amygdala blood flow versus $1.2 + 1.4\%$ in controls (effect size 1.39). With two tails, an alpha value set at 0.05 and a power of 0.80, 10 subjects are needed in each group (VNS v sham) to show a significant difference between patients and controls (i.e. group by condition interaction). The number of subjects in each group will therefore be adequate to answer the questions proposed in this study.

- 17.2 All study staff will take required training prior to working with participants and/or PHI. All data will be kept in either locked offices in secure buildings or online via Redcap or on a password restricted research server. A certificate of confidentiality will be in place. Confidentiality will be assured by the use of subject codes when possible rather than personal identifiers. After the study is completed, the study database will be secured, and information will only be entered using subject identifier codes rather than personal identifiers. Published results will be presented as group data, without identifiers.
- 17.3 A (bi) weekly meeting with the staff, Study Coordinator and the PI is held to discuss any issues that may arise. A review of data is done for accuracy and protocol compliance. Data collection forms are verified for accuracy before storing in database. Describe any procedures that will be used for quality control of collected data.
- 17.4 Describe how data or specimens will be handled study-wide:
 - Study ID, date of visit, and type of sample will be included for each specimen
 - Specimens will be stored in a -80 freezer at EP12 or RSPH
 - Specimens will be stored until they are fully utilized for testing
 - The [name] Lab and the study team will have access to the data and/or specimens

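### The only threshold given for the exploratory PET maps contradicts itself: one cutoff is labelled both uncorrected and corrected, and the p inequality is reversed

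*Combined protocol and SAP*

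**What the plan says.** Section 17.1 of the combined protocol and SAP (under 17.0, Data Management and Confidentiality) adds an exploratory image analysis to the blood flow ANOVA. Its stated purpose is to "look for additional areas of activation for the purpose of generating hypotheses for future studies".

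- **Model:** "Images will be then analyzed using the general linear model of Friston for statistical analysis".
- **Directions examined:** "Areas of increased and decreased blood flow within patient group will be examined", along with the condition-by-group interaction.
- **Map and region:** "Images of t statistic will be created and surveyed for hypothesized regions (i.e. medial prefrontal cortex").
- **Threshold:** the maps are read where "uncorrected z score values are greater than 2.86 (corresponding to a corrected p value of > 0.005").

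No other threshold is given for these maps. The section states no multiplicity correction, search volume or sidedness for them. Two tails are mentioned only in the sample size paragraph.

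**The concern.** A single cutoff cannot be both uncorrected and corrected unless a correction is described that links the two, and none is. Naming the general linear model identifies a model, not a way of controlling error over many voxels or regions. The direction of the p statement is also impossible as printed, because a larger z means a smaller p.

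What is at stake is how peaks are described in a report. This is the maps' only stated decision rule and it is applied to the hypothesized regions. Someone relying on the parenthesis could present peaks that passed an uncorrected cutoff as significant after correction at 0.005. A second, smaller problem is that the images are of t while the cutoff is a z, with no conversion mentioned, so an analyst cannot be sure which rule to apply.

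**Working it through.** **Inputs.** From section 17.1: cutoff 2.86, called an uncorrected z; p of 0.005, called corrected and printed with a greater-than sign; t images; increases and decreases both examined; sidedness, correction method and search volume not stated. From sections 1.0 and 12.1: N = 20 in Study #2. From Calculation of Sample Size: 10 per group.

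**1. Can 0.005 be reproduced from z = 2.86?**
- One-sided: p = 1 − Φ(2.86) = 0.00212.
- Two-sided: p = 2 × 0.00212 = 0.00424.
- In reverse, p = 0.005 corresponds to z = 2.576 one-sided or 2.807 two-sided.

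Neither version gives 0.005 exactly. However, 0.00424 is below 0.005, so 2.86 does satisfy an uncorrected two-sided p < 0.005.

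**2. Direction.** Two-sided p is 0.0050 at z = 2.807 and 0.0042 at z = 2.86, so p falls as z rises. Values above the cutoff have p below the matching level, not above it.

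**3. Could 0.005 be a corrected p?** For m independent tests, corrected p = 1 − (1 − p)^m. Setting this to 0.005 and solving for m:
- Two-sided: m = ln(0.995)/ln(1 − 0.004236) = 1.18.
- One-sided: m = ln(0.995)/ln(1 − 0.002118) = 2.36.

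Bonferroni gives the same: 0.005/0.004236 = 1.18 and 0.005/0.002118 = 2.36. No whole number of tests yields 0.005. A corrected p below 0.005 would hold for one two-sided test, or for at most two one-sided tests. Since the plan gives no search volume, the test counts below are assumptions that show the range:

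| Assumed independent tests | Corrected p, two-sided | Corrected p, one-sided |
|---|---|---|
| 2 | 0.0085 | 0.0042 |
| 10 | 0.042 | 0.021 |
| 50 | 0.19 | 0.10 |

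**4. Could 2.86 be a t cutoff?** The images are t maps, so this was tried.
- 19 df (20 subjects, a within-subject contrast): P(T > 2.86) = 0.00501 one-sided and 0.0100 two-sided. The one-sided 0.005 critical value is 2.861.
- 18 df (10 v 10): P(T > 2.86) = 0.0052 one-sided, with critical value 2.878.

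On 19 df, t = 2.86 has the tail area of z of about 2.58. Against a true z of 2.86 the one-sided tail area differs by a factor of 0.00501/0.00212 = 2.4, so the two readings would not pass the same peaks.

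**The case against.** The strongest reply is that little turns on this. The maps are declared hypothesis-generating, and no endpoint, ANOVA or sample size depends on the cutoff. The operative rule, 2.86 on values expressly called uncorrected, can be applied whatever the parenthesis says. The reversed sign may not be the authors' error at all: the sample size paragraph of the same section prints a plus where plus-minus is evidently meant, so symbols here may have been misread. Most of this stands, and it limits the point to a minor one. It does not remove the label conflict, which is in words and would survive any repair of symbols.

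A reader might infer that the plan also makes a material arithmetic error in pairing 2.86 with 0.005. The documents do not support that as a main criticism. Read as a two-sided z, which is natural when both directions are examined, the cutoff meets 0.005. Read as a one-sided t on 19 df, it matches 0.005 almost exactly.

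A reader might equally infer that 2.86 is simply a t cutoff mislabelled as z. That is plausible but unproven: neither 19 df nor a one-sided test is stated. Even if it were so, the p would still be uncorrected and the printed inequality still reversed.

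**Conclusion.** The threshold statement is wrong as written. The main fault is that one cutoff carries two incompatible labels with no correction method or search volume. The reversed inequality comes second, with slightly less certainty because of possible symbol misreading. The unclear statistic is a secondary point: as a z, 2.86 is uncorrected p = 0.0021 one-sided or 0.0042 two-sided; as a t on 19 df, an inference, it is one-sided p = 0.0050.

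The consequence is minor and limited to how exploratory peaks are described. It would go too far to say that the cutoff is slightly strict: that holds for a z, but not for a one-sided t on 19 df. The corrected p values for assumed numbers of tests show only that the corrected label depends on a search volume the plan does not give; they do not estimate this study's error rate.

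**What to change.** Amend the sentence in section 17.1 as follows.

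1. State whether 2.86 is a z or a t cutoff. If z, say that the t maps are converted to z; if t, give the df for each contrast.
2. State whether the test is one- or two-sided.
3. Replace the greater-than sign with a less-than sign in the p statement.
4. Delete the corrected label, or else specify the correction method and the search volume.
5. Say that peaks passing only this cutoff will be reported as uncorrected and hypothesis-generating.

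If 2.86 is kept as a two-sided z, describing it as uncorrected two-sided p < 0.005 is sufficient, and no new p value is needed.

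The cost is wording only, with no new data. Peaks lose the corrected label unless a correction is specified. The list of peaks stays the same only if the maps were in fact to be thresholded at z = 2.86. If they were to be cut at t = 2.86 on 19 df, moving to z = 2.86 would be stricter and could drop peaks.

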2.0 Objectives*

- 2.1 The purpose of this study is to measure neural and biomarker correlates of vagal nerve stimulation (VNS) in men and women with a history of Opioid Use Disorders (OUDs). In the UG3 phase we will have two studies, Study #1 will be to optimize dosing (N=20) and Study #2 to measure brain and biological correlates of nVNS versus sham in conjunction with exposure to drug use cues (N=20). We will proceed to the UH3 phase which is a larger study in OUD patients if the goals of the UG3 phase are met per NIDA. Only the UG3 phase is covered here.
- 2.2 Brain function will be measured with positron emission tomography (PET) and biomarkers will be measured in blood, with an assessment of a broad range of stress responsive sympathetic, hormonal and immune markers
- 2.3 We hypothesize a decrease in sympathetic function and enhanced anterior cingulate function with VNS.

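### The 80% power claimed for anterior cingulate activation, nVNS versus sham, rests on an amygdala, fear-task, patient-versus-control effect size with no argument that it carries over

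*Combined protocol and SAP*

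**What the plan says.** The sample-size paragraph in Section 17.1 (Calculation of Sample Size) opens by naming its target: "For calculation of sample size needed for PET measurement of anterior cingulate activation". It then gives its source: "we used values for blood flow in the amygdala (scaled to whole brain blood flow) based on previous pilot data". The pilot figures are a 6.9 + 4.8% rise in amygdala blood flow with fear-related tasks against 1.2 + 1.4% in controls, reported as an effect size of 1.39. With two-sided alpha 0.05 and power 0.80, it concludes that "10 subjects are needed in each group (VNS v sham) to show a significant difference between patients and controls", described as a group by condition interaction. It ends: "The number of subjects in each group will therefore be adequate to answer the questions proposed in this study".

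The study itself is described differently elsewhere:

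- Section 2.3: "We hypothesize a decrease in sympathetic function and enhanced anterior cingulate function with VNS".
- Section 6.2: "Study #2 is also in patients with OUDs whose aim is to measure brain and biological correlates of nVNS versus sham", together with exposure to drug-use cues, N=20, with random assignment of active and sham devices.
- Section 6.5: the tasks are neutral and opioid-use videos.
- Section 10.2: Study #2 takes people who "meet criteria for OUDs based on DSM-5 criteria; 2) have IV access". No non-patient group is described.

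**The concern.** A power statement is only as good as the effect size behind it, and that effect size has to belong to the comparison being made. Here it belongs to another brain region, another task and another contrast. How far patients differ from controls in their response to fear says nothing direct about how far a device shifts the response to drug cues among patients who are randomised to it or to sham.

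This is the only sample-size justification in the documents, and it ends by declaring the numbers adequate for the study's questions. A reader will take the nVNS-versus-sham anterior cingulate comparison to have 80% power. If the true effect is smaller than the borrowed one, a null result could be misread as absence of effect. That matters because progress to the larger UH3 study depends on the UG3 goals being met (Section 2.1). The adequacy sentence also reaches further than the calculation: craving, pre-ejection period and PPG amplitude are named with the primary endpoint in Section 4.1, and no power basis is given for any of them.

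**Working it through.** **Inputs from Section 17.1.** Effect size d = 1.39; two-sided alpha 0.05; power 0.80; n = 10 per group, equal allocation. Pilot values 6.9 + 4.8% and 1.2 + 1.4%, read here as mean ± SD.

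**1. The plan's own figure.** For a two-sample t-test with n per group, the degrees of freedom are 2n − 2 and the noncentrality is d × √(n/2).

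- Solving for 80% power at d = 1.39 gives n = 9.19, which rounds up to 10.
- At n = 9, power is 0.790. At n = 10, noncentrality is 1.39 × √5 = 3.11 on 18 df, and power is 0.836.

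The step from 1.39 to 10 per group is therefore right.

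**2. Does 1.39 describe the planned comparison?**

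| Feature | Source of 1.39 | Study #2 |
|---|---|---|
| Region | Amygdala | Anterior cingulate |
| Task | Fear-related | Neutral and opioid-use videos |
| Contrast | Patients versus controls | nVNS versus sham, all patients |

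The paragraph does not name the pilot index group. That it was patients is inferred from the sentence that follows the figures. The region and task mismatches do not depend on that inference.

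**3. What 10 per group can detect.** The documents give no mean, SD or effect size for the anterior cingulate under nVNS versus sham, so the effects below are assumptions.

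- Smallest d with 80% power on 18 df: 1.325. As a share of the borrowed value, 1.325 / 1.39 = 0.95, so about 95% of it would have to carry over.
- Half-width of the 95% confidence interval: t(0.975, 18) × √(2/10) = 2.101 × 0.447 = 0.94 SD.

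| Assumed d | Power at 10 per group | n per group for 80% |
|---|---|---|
| 1.0 | 0.562 | 17 |
| 0.8 | 0.395 | 26 |
| 0.5 | 0.185 | 64 |

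**4. Sensitivity to the planned model.** Section 17.1 plans an ANOVA with "absolute blood flow during control task as well as study group as explanatory variables", blocked on past alcohol exposure and adjusted for whole-brain flow. Assume three fixed terms (control-task flow, whole-brain flow, a one-df alcohol block), balanced between groups. Residual df = 20 − 2 − 3 = 15, and residual SD = √(1 − R²) of the raw SD, where R² is the assumed share of variance explained.

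| Assumed R² | Residual SD | Detectable difference (raw SD) | Power at 0.8 | CI half-width (raw SD) |
|---|---|---|---|---|
| 0 | 1 | 1.34 | 0.388 | 0.95 |
| 0.25 | 0.866 | 1.16 | 0.489 | 0.83 |
| 0.50 | 0.707 | 0.95 | 0.658 | 0.67 |

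Any covariates added by the plan's data-driven selection rule are left out.

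**5. A side note that is not an error.** With equal weights the pooled SD is √((4.8² + 1.4²)/2) = 3.54, and 5.7 / 3.54 = 1.61. The printed 1.39 implies a pooled SD of 5.7 / 1.39 = 4.10. Unequal pilot groups could give that; for example, 13 and 6 give √((12 × 4.8² + 5 × 1.4²)/17) = 4.10. The pilot sizes are not stated, and 1.39 is the more conservative value.

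**The case against.** The best defence is that the proxy is disclosed. The paragraph says openly that amygdala values are used, and borrowing an effect size is common when direct data are lacking. Section 3.2 also reports the team's own finding that nVNS enhances anterior cingulate responses to stress in traumatised people and patients with PTSD, which is the right region and the right intervention. The study is a small early phase meant to map physiology, its arithmetic is correct, and nothing shows the true power to be below 80%. The effects of 1.0, 0.8 and 0.5 are generic, and covariate adjustment could bring the detectable difference below 1 SD.

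Part of this stands. The power is unsupported rather than shown to be wrong, the smaller effects are illustrations, and useful covariates would help. But disclosing a proxy does not justify it when three features change at once. Section 3.2 supports the direction of an effect but gives no size or variance, and the calculation does not use it. The paragraph also claims no gain from adjustment. A small mapping study needs no power claim; this one makes one and adds an adequacy statement.

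**Conclusion.** The concern holds. The stated 80% power belongs to a comparison that Study #2 does not make, and the documents give no effect size for the one it does make. What can be said is that 10 per group has 80% power for a standardised nVNS-sham difference of about 1.32 or more, under an unadjusted two-sample t-test with equal variances, 20 completers and two-sided alpha 0.05. Under the assumed covariate gains the detectable difference ranges from 1.34 down to 0.95 raw SD. The true power cannot be worked out from the documents. The claim should be corrected; the sample size need not change.

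**What to change.** Keep N=20. In Section 17.1, delete the amygdala and patient-versus-control figures and the closing adequacy sentence, and put in their place:

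> With 10 per group and two-sided alpha 0.05 (unadjusted two-sample t-test), the study has 80% power only for a standardised nVNS-sham difference in anterior cingulate blood-flow change of about 1.32 or more. Under assumed effects of 1.0, 0.8 and 0.5, power is 56%, 40% and 19%, and the 95% confidence interval half-width is about 0.94 SD. Covariate adjustment will change these figures.

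If the team holds anterior cingulate data behind the statement in Section 3.2, with means and SDs for nVNS and sham, a calculation based on those data and an explicit argument for applying them to drug cues would also meet the point.

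The cost is protocol wording only: no more patients and no change to procedures or analysis. The price is a less favourable power statement.
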